Title	Evaluation of a Millimeter Wave Emission Bracelet -Type Medical Device for Improving Parkinson's Disease Symptoms: Multicenter, Double-blind Randomized Controlled Trial
Acronym	ВОМР
Sponsor	Hôpital Fondation Adolphe de Rothschild
Principal Investigator	[name]
Research justification	Idiopathic Parkinson's disease is a common neurodegenerative disorder, with a prevalence of approximately 2% among individuals over 65 years old in France, corresponding to 120,455 patients (ranging from 94,861 to 151,896) [1]. This disease primarily affects the dopaminergic pathway (damage to the nigrostriatal pathway leads to cardinal symptoms such as rigidity, bradykinesia, and tremor), but it also impacts other systems: cholinergic, noradrenergic, and serotonergic [2]. The symptoms of Parkinson's disease are therefore motor, initially with a good response to dopaminergic treatments, but also non-motor, including sleep disturbances, loss of smell, cognitive, psychiatric, digestive, urinary, dysautonomic, and painful issues [3]. All these symptoms contribute to a significant reduction in the quality of life of patients, who, together with clinicians, are still constantly seeking solutions to improve management. Continuous dopaminergic stimulation is desirable to reduce motor fluctuations in patients, who experience motor fluctuations such as wearing-off, dyskinesias, and freezing [4]. Invasive techniques (deep brain stimulation, gamma knife lesioning, ultrasound) or devices that are heavy, invasive, and costly (duodopa pumps, apokinon pumps) have provided benefits for patients [5]. There is an ongoing need to explore clinical improvements using less expensive and lighter devices. The Remedee Endorphin Band is a device that emits electromagnetic waves in the millimeter waveband on the inner side of the wrist, an area rich in nerve endings. The device stimulates subcutaneous nerve endings and activates a physiological response that triggers the release

of endorphins in the brain. Endorphins are involved in several physiological processes, including pain control. Mu-opioid receptor (MOR) agonists not only relieve pain but also have effects related to dopaminergic mesolimbic pathways [6,7]. Indeed, the opioid and dopaminergic systems are closely linked at the cellular level [8]. Endorphins, by inhibiting the release of the neurotransmitter GABA when binding to the μ receptor, are also related to an increase in dopamine.

- 14) Describe the effectiveness perceived by the patient after discontinuing the use of the device: bi-weekly follow-up phone calls for 2 months after use.
- 15) Evaluate the tolerance of the medical device.
- 16) Evaluate the acceptability and usability of the medical device.
- 17) Description of the device usage compliance.

Secondary Outcome Measures:

- 1. Average change in MDS-UPDRS III score under ON Dopa conditions
- 2. Average change in MDS-UPDRS I score (Annex 2) under ON Dopa conditions
- 3. Average change in MDS-UPDRS II score (Annex 3) under ON Dopa conditions
- 4. Average change in MDS-UPDRS IV score (Annex 4) under ON Dopa conditions
- 5. Average change in Parkinson Disease Questionnaire-39 (PDQ-39) score (Annex 5) under ON Dopa conditions
- 6. Average change in King's PD Pain Scale (KPPS) score (Annex 6) under ON Dopa conditions
- 7. Change in time (in seconds) required for the Stand-Walk-Sit (SWS) test (Annex 7) under ON Dopa conditions. This change will be expressed as a percentage change in time, defined as the difference between the time required at baseline and 2 months after randomization, divided by the baseline time.
- 8. Slope of the evolution in the average number of steps per week measured using an activity tracker (Fitbit 4) between -2 weeks and +8 weeks, for patients who agreed to wear this second bracelet.
- 9. Evolution of the average number of hours of weekly sleep and average weekly hours of deep, paradoxical, light sleep, and nighttime wakefulness, measured

2020-A02551-38

	using an activity tracker (Fitbit 4) between -2 weeks and +8 weeks, for patients who agreed to wear this second bracelet. 10. Evolution of the average weekly heart rate measured using an activity tracker (Fitbit 4) between -2 weeks and +8 weeks, for patients who agreed to wear this second bracelet. 11. Percentage of patients with no change (in drug type or dosage) or a decrease in medication dosage. 12. Score on the Clinical Global Impression of Change (CGI) questionnaire (Annex 8) at M2, taking J0 as the reference point, reported in person or by phone by the person identified by the patient as the primary caregiver. 13. Score on the Clinical Global Impression of Change (CGI) questionnaire (Annex 8) at M2, taking J0 as the reference point. 14. CGI score at M6, taking M2 as the reference, then every 2 weeks for two months via phone interviews. For phone assessments, the patient will be asked to use the situation from two weeks prior (during the previous CGI score evaluation) as the reference. 15. Description of adverse events reported during the study: number, intensity, severity, duration in each of the two arms. 16. Acceptability and usability questionnaire completed by the patient at M6 (Annex 10). 17. Compliance assessed using the medical device log file (number of sessions/day, duration of sessions, start and end times, pause times).
Study design	Multicenter, controlled, randomized, parallel two- arm, double-blind efficacy trial. Randomization will be performed with a 1:1 ratio and will be stratified by center.
Population	Patients will be recruited via neurology consultations for the management and monitoring of their Parkinson's disease.
Selection criteria	 Patient aged over 18 years Follow-up for Parkinson's disease with progression for more than 5 years Stable treatment for at least 3 months Maintained sufficient autonomy to participate in the study Non-faller: Hoehn and Yahr score in ON DOPA <4 (Annex 9) Informed and has signed consent to participate in the study Affiliated or beneficiary of a social security scheme

	Negative urinary pregnancy test for women who are not postmenopausal
	Exclusion Criteria
	 Genetic forms of the disease EVA > 7 in the previous week Moderate to severe cognitive disorders Pathology or condition (other than Parkinson's disease) that could cause motor disturbances Allergy to metals and/or silicone Dermatological pathology on the wrists, such as weeping dermatosis, excessive sweating, or an unhealed lesion Metal object on one of the wrists (implanted metal, piercing) Presence of a tattoo on one of the wrists Wrist circumference <14.5 cm or >21 cm, i.e., wrist size incompatible with the device model Inability of the patient to apply and/or wear the medical device Patient under legal protection Pregnant or breastfeeding woman Secondary Exclusion Criteria: None specified in the protocol
	Experimental Therapeutic Intervention Medical device Remedee Endorphin Band with millimeter wave emission activated for a duration of 6 months, to be used according to the following schedule: one 30-minute session in the morning and one session in the evening. Additional sessions may be added if desired by the patient, up to a maximum of 4 sessions per day.
Trial procedures	Control Therapeutic Intervention Medical device Remedee Endorphin Band without millimeter wave emission for two months, followed by the Remedee Endorphin Band with millimeter wave emission activated for a duration of 4 months, to be used according to the following schedule: one 30-minute session in the morning and one session in the evening. Additional sessions may be added if desired by the patient, up to a maximum of 4 sessions per day.
Conduct of the trial	Patients seen during consultations/Day Hospital and meeting the inclusion and non-inclusion criteria will be offered the opportunity to participate in the study. If they agree, a visit will be scheduled (within 2 to 4 weeks) to perform the various tests and provide the medical device to the patient (VERUM or SHAM according to the randomization group).

Patients will be randomized into two parallel groups (1:1 ratio) via an online randomization module. The doctor enrolling the patient in the study will not be aware of the randomization group.

- Experimental Group (VERUM): Provision of an active medical device for a period of 2 months. Then, provision of a second active medical device for a duration of 4 months.
- Control Group (SHAM): Provision of an inactive medical device for a duration of 2 months, followed by the provision of an active medical device from Month 2 to Month 6 after enrollment.

Inclusion Visit (J0-2 to -4 weeks)

- Verification of inclusion and non-inclusion criteria
- Information and obtaining written informed consent from the patient
- Information to the patient regarding the Fitbit 4 and the option to use it
- Trial fitting of the Remedee Endorphin Band device

Visit 1 (J0)

- Confirmation of patient's willingness to participate
- Randomization
- Provision of the medical device and instructions on its use
- Administration of the various assessment tests (if necessary, after administration of Modopar dispersible):
 - o MDS-UPDRS (I, II, III, and IV)
 - o PDQ39
 - o KPPS
 - o SWS

Phone Call at J7 and M1: Verification that the patient does not encounter any difficulties in using the device (call by the TEC)

Visit 2 (M2)

- Administration of the various assessment tests (if necessary, after administration of Modopar dispersible):
 - o MDS-UPDRS (I, II, III, and IV)
 - o PDQ39
 - o KPPS
 - o SWS
- CGS score from the caregiver (in-person or by phone)
- CGS score from the patient

	 Retrieval of usage data from the medical device (log file) Retrieval of the first medical device (active or inactive) and provision of an active medical device to all patients. Visit 3 (M4) Administration of the various assessment tests (if necessary, after administration of Modopar dispersible): MDS-UPDRS (I, II, III, and IV) PDQ39 KPPS SWS Retrieval of usage data from the medical device (log
	file) Visit 4 (M6) • Administration of the various assessment tests (if necessary, after administration of Modopar dispersible):
	 KPPS KPPS SWS Administration of the acceptability and usability questionnaire for the medical device CGS score from the patient Retrieval of usage data from the medical device (log file) Retrieval of the millimeter-wave emitting bracelet Retrieval of the Fitbit4 for patients who accepted its use
	Phone Calls at M6+2 weeks, M6+4 weeks, M6+6 weeks, and M6+8 weeks: CGS score from the patient, and at M6+8 weeks, the patient will also be asked if they would have liked to continue using the medical device bracelet.
Sample size	60 (30 per arm)
Statistical analysis	The primary endpoint will be analysed using logistic regression with a centre effect.
Planning	Enrollement : 24 months Study participation for each patient : 8 months Total study length : 32 months

# 1. Statistical Analysis Plan from the Protocol

### 1.1. Objectives

### 1.1.1. Primary Objective

To assess the effectiveness of two months of use of the medical device Remedee Endorphin Band in the significant improvement of motor disorders in patients with Parkinson's disease.

### 1.1.2. Secondary Objectives

To evaluate the effectiveness of two months of use of the Remedee Endorphin Band on:

- 1. The motor disorders of patients;
- 2. Non-motor experiences in daily life;
- 3. Motor experiences in daily life;
- 4. Motor complications;
- 5. Quality of life;
- 6. Pain;
- 7. Walking;
- 8. The evolution of the average number of steps per week (only for patients who agreed to wear a second specific bracelet);
- 9. The evolution of sleep (only for patients who agreed to wear a second specific bracelet);
- 10. The evolution of heart rate (only for patients who agreed to wear a second specific bracelet);
- 11. The medication regimen;
- 12. The effectiveness of the treatment as perceived by the primary caregiver;
- 13. The effectiveness of the treatment as perceived by the patient.

After two months of use, the medical devices will be collected, and new active medical devices will be provided to the patients in both arms.

The elements evaluated for the primary objective and secondary objectives 1 to 10 will be described at M4 and M6 to document the evolution of the effect of the medical device using millimeter wave stimulation.

- 14. To describe the effectiveness perceived by the patient after discontinuing the device use: biweekly phone follow-ups for 2 months after use.
- 15. To assess the tolerance of the medical device.
- 16. To assess the acceptability and usability of the medical device.
- 17. Description of compliance with the use of the device.

### 1.2. Judgment Criteria

### 1.2.1. Primary Judgment Criterion

Comparison between the two treatment arms (VERUM bracelet and SHAM bracelet) of the percentage of patients showing an improvement of at least -3.25 points in the Movement Disorder Society – Unified Parkinson's Disease Rating Scale part III (MDS-UPDRS III), 2 months after randomization.

The MDS-UPDRS III score (Appendix 1) will be assessed in ON Dopa conditions, blind to the randomization arm.

### 1.2.2. Secondary Judgment Criteria

1. Mean change in MDS-UPDRS III score in ON Dopa conditions.

- 2. Mean change in MDS-UPDRS I score (Appendix 2) in ON Dopa conditions.
- 3. Mean change in MDS-UPDRS II score (Appendix 3) in ON Dopa conditions.
- 4. Mean change in MDS-UPDRS IV score (Appendix 4) in ON Dopa conditions.
- 5. Mean change in the Parkinson Disease Questionnaire -39 (PDQ 39) score (Appendix 5) in ON Dopa conditions.
- 6. Mean change in King's PD Pain Scale (KPPS) score (Appendix 6) in ON Dopa conditions.
- Change in the time (in seconds) required for the Stand-Walk-Sit (SWS) test (Appendix 7) in ON Dopa conditions. This change will be expressed as a percentage of time change, defined as the difference between the time required at baseline and 2 months after randomization, divided by the baseline time.
- 8. Slope of the change in the average number of steps per week measured with an activity bracelet (Fitbit 4) between D-2 weeks and D+8 weeks, for patients who agreed to wear this second bracelet.
- 9. Evolution of the average number of hours of weekly sleep and the average weekly hours of deep, paradoxical, light sleep, and night wakefulness, measured with an activity bracelet (Fitbit 4) between D-2 weeks and D+8 weeks, for patients who agreed to wear this second bracelet.
- 10. Evolution of the average weekly heart rate measured with an activity bracelet (Fitbit 4) between D-2 weeks and D+8 weeks, for patients who agreed to wear this second bracelet.
- 11. Percentage of patients without any modification (in drug molecule or dosage) in their medication regimen or with a reduction in medication dosage.
- 12. Score on the Clinical Global Impression of Change (CGI) questionnaire (Appendix 8) at M2, using the baseline (D0) provided in person or by phone by the person designated as the primary caregiver.
- 13. Score on the CGI questionnaire (Appendix 8) at M2, using D0 as the reference.
- 14. CGI score at M6, using M2 as the reference, and then every 2 weeks for two months through phone interviews. For phone evaluations, the patient will be asked to use the situation two weeks prior (during the previous CGI score evaluation) as the reference.
- 15. Description of adverse events reported during the study: number, intensity, severity, duration in each arm.
- 16. Acceptability and usability questionnaire completed by the patient at M6 (Appendix 10).
- 17. Compliance evaluated based on the medical device log file (number of sessions/day, session duration, pause times).

# 1.3. Reminder on the Calculation of the Required Sample Size

This is a pilot study, as the bracelet has not yet been studied in patients with motor disorders in Parkinson's disease. We therefore planned to include 30 subjects per group.

Since the percentage of patients improving in the control arm is expected to be close to zero, a sample size of 30 patients per arm will allow us to detect a difference in percentage of 15% of improved patients versus 0.1% in the control arm, with a power of 80% and a bilateral alpha risk of 5%.

Patients lost to follow-up between the inclusion visit and randomization will be replaced.

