# 1.4.3. Analysis of the Primary Judgment Criterion

The primary judgment criterion will be analyzed using logistic regression with a center effect. A Per Protocol sensitivity analysis will be conducted, including only patients who adhered to the medical device. A patient will be considered adherent if they completed more than 80% of the planned sessions, considering a low-frequency usage of 2 sessions per day.

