# **1.5. Statistical Significance Level**

Alpha risk set at 5%.

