### 1.6. Method for Handling Missing, Unused, or Invalid Data

Analyses will be performed on complete data. If missing data for the primary judgment criterion exceeds 10%, a sensitivity analysis will be conducted after multiple imputation.

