### Analysis of the Primary Criterion:

All patients in the study were included by the HFAR center, so a fixed-effects logistic regression was conducted instead of the initially planned random-effects center logistic regression.

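### The stated 80% power rests on a 0.1% sham response rate supported only by an expectation, and on a logistic-regression test that the SAP does not name

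*SAP*

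**What the plan says.** SAP section 1.3 calls the trial a pilot, sets 30 patients per group for that reason, and then says what this size can detect: "15% of improved patients versus 0.1% in the control arm, with a power of 80% and a bilateral alpha risk of 5" per cent. It names no formula or software. The support given for the control rate is an expectation: "Since the percentage of patients improving in the control arm is expected to be close to zero". The protocol synopsis gives only 60 patients, 30 per arm.

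On the analysis, SAP section 1.4.3 says "The primary judgment criterion will be analyzed using logistic regression with a center effect". Section 2 (*Analysis of the Primary Criterion*) reports that a single centre recruited all patients, "so a fixed-effects logistic regression was conducted instead of the initially planned random-effects center logistic regression". Neither says whether the arm effect is tested by a Wald, likelihood-ratio or score statistic, or what happens if one arm has no responder. Section 1.5 adds "Alpha risk set at 5" per cent.

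On losses, section 1.3 says "Patients lost to follow-up between the inclusion visit and randomization will be replaced" and is silent on losses after randomization. Section 1.6 says "Analyses will be performed on complete data", with multiple imputation as a sensitivity analysis when more than 10% of primary outcomes are missing.

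**The concern.** A power statement belongs to a particular test under particular rates. Here the assumed control rate is so low that the usual tests from one logistic model no longer agree, and the SAP does not choose among them. The control rate is also the input to which the power is most sensitive. The endpoint is a 3.25-point improvement on a rating scale, which some sham patients could reach through ordinary variability or a placebo response.

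What is at stake is how a non-significant result is read. Someone who takes the 80% at face value will treat such a result as fairly good evidence against a 15-point effect. Depending on the test and the true sham rate, it could be much weaker evidence than that.

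**Working it through.** **Inputs.** Rates 0.15 and 0.001, 30 per arm, two-sided 5% (SAP 1.3). Logistic regression with treatment arm only, since all patients came from one centre (SAP section 2). Sham rates other than 0.1% are assumptions; the documents give none.

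**Reproducing the 80%.** Arcsine approximation:
- h = 2·asin(√0.15) − 2·asin(√0.001) = 0.795 − 0.063 = 0.732.
- Power = Φ(0.732·√(30/2) − 1.96) = Φ(0.876) = 80.9%.
- Patients needed per arm = 2·((1.96 + 0.8416)/0.732)² = 29.3, rounded up to 30.

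The usual normal formulas do not give 80%: pooled 59.2% (49 per arm needed), unpooled 62.4% (46 per arm). Arcsine is therefore the likely source, but this is inferred.

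**Exact power at the stated rates.** P(no sham responder) = 0.999³⁰ = 0.970, and P(exactly one) = 30 × 0.001 × 0.999²⁹ = 0.029. These two cases cover almost everything. The critical value is 3.84.
- *Sham 0 of 30.* Likelihood-ratio: 2 verum responders give 2.84 and 3 give 4.32, so it rejects from 3. Pearson: 3 give 3.16 and 4 give 4.29, so it rejects from 4. Wald never rejects, because the estimated odds ratio is infinite; a fit to 5 of 30 versus 0 of 30 gives Wald p = 0.999.
- *Sham 1 of 30.* Likelihood-ratio and Pearson reject from 6 verum responders, Wald from 7.
- For verum ~ Binomial(30, 0.15): P(≥3) = 0.849, P(≥4) = 0.678, P(≥6) = 0.289, P(≥7) = 0.153.

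| Test | Calculation | Power |
|---|---|---|
| Likelihood-ratio | 0.970 × 0.849 + 0.029 × 0.289 | 83.2% |
| Score (Pearson) | 0.970 × 0.678 + 0.029 × 0.289 | 66.7% |
| Wald | 0.029 × 0.153 | 0.45% |

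Full enumeration of all tables gives the same figures.

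**Type I error of the likelihood-ratio test.** At common response rates of 0.1, 1, 2 and 3% it is 0.0, 0.5, 2.4 and 4.8%. At 5, 6.5 and 10% it is 8.3, 8.9 and 7.5%. Pearson never exceeds 5.5%.

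**Sensitivity to the sham rate** (same 15-point difference, 30 per arm, exact):

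| Assumed sham rate | Likelihood-ratio | Pearson | Wald |
|---|---|---|---|
| 5% | 48% | 45% | 18% |
| 10% | 37% | 34% | 23% |
| 20% | 28% | 25% | 23% |

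As the sham rate rises, the tests converge and power falls whichever is used.

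**Missing outcomes.** As an assumed example, 27 analysed per arm gives 78% (likelihood-ratio) or 58% (Pearson) at 15% versus 0.1%.

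**What a null result would exclude.** With 30 per arm and equal responders, the Miettinen-Nurminen 95% interval for the risk difference is ±11.5 points at 0 versus 0, ±13.9 at 1 versus 1, ±15.9 at 2 versus 2 and ±21.0 at 6 versus 6. A 15-point benefit is excluded in the first two cases but not in the last two. The interval also exists with one empty arm: 4 versus 0 gives 1.0 to 29.8 points.

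**The case against.** The strongest reply is that the 80% is sound on its own terms. It reproduces, and one standard test of the planned model, the likelihood-ratio test, exceeds it at the design rates. The trial is also a declared pilot whose size came from that status, with the power sentence only describing it. All of this stands, and it rules out calling the sample size calculation wrong.

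The reply also blocks four stronger readings that a reader might infer.
- *That the true power is about two in three because the likelihood-ratio test does not hold 5%.* This mixes scenarios. At the design rate its type I error is near zero; the inflation appears at common rates above about 3%, where the sham rate rather than the test mainly limits power.
- *That the trial had almost no power.* This needs a Wald p-value and an empty or nearly empty sham arm. The documents show neither. SAP section 2 reports dropping the logistic model for criterion 11 but mentions no such difficulty with the primary criterion. That is weak evidence, but it points away from the extreme case.
- *That the 10% missing-data trigger affects primary power.* It does not. Imputation is a sensitivity analysis only, so the primary analysis uses complete cases at any level of missingness.
- *That no basis for 0.1% exists.* Parts of the SAP were not available for this review, and the protocol text is a synopsis. One can say only that the text supplied gives none.

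What remains after the reply is the unnamed test, the unsupported sham rate and the lack of any margin for post-randomization losses.

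**Conclusion.** The concern holds in a limited form. The 80% is a valid approximation under the stated rates, but the SAP does not tie it to the test that produces the primary p-value. At those rates, exact power is 83%, 67% or under 1% for the three usual tests.

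The sham rate matters more. At assumed sham rates of 5 to 20% with the same 15-point difference, power lies between 18 and 48% over all three tests, and at 20% it is only 23 to 28%. These are sensitivity figures, not forecasts; the documents do not say what the sham rate is likely to be.

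The calculations assume one centre, no covariates and, unless stated otherwise, 30 analysed per arm. This is a matter of specification and interpretation, and it does not invalidate the trial.

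**What to change.** Keep the 60 patients and leave SAP section 1.3 unchanged, since it records the protocol's plan. In SAP section 2 and in the report:

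1. State which test statistic gave the primary p-value. Restate the exact power of that test for 15% versus 0.1%, with a short range over assumed sham rates such as 5, 10 and 20%. Confirm whether the 80% came from an arcsine approximation. If the test was likelihood-ratio, give its type I error range as well.
2. Report the risk difference with a score-type (Miettinen-Nurminen) 95% confidence interval, and interpret a non-significant result from that interval.
3. If the test was Wald and an arm has no or very few responders, add a Firth penalised likelihood-ratio result, labelled post hoc because the SAP does not plan it.

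The cost is one short paragraph, one confidence interval and at most one extra model run, with no added patients. The drawbacks are that the stated power will probably look less favourable, and that any added test is post hoc and must be presented as such.
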